4.3 Exclusion criteria

A potential subject who meets any of the following criteria will be excluded from participation in this study:

- Aged over 18 years or under 8 years of age
- Does not have spina bifida

4.4 Sample size calculation

Since this is a descriptive study no minimal sample size is required.

However, our aim is to include 500 patients.

4.5 (Planned) start date

Depending on the approval of the NWTC.

Start date 01.01.2023.

4.6 (Planned) end date

The digital questionnaire will be available for 3 months.

5 Methods

5.1 A digital survey has been created on Surveymonkey: <https://www.surveymonkey.com/r/7WSB9S9>

This digital survey includes a primary survey regarding basic demographic features, medical treatment and organization of care. This survey was constructed by the EAU guidelines panel and the IFSBH patient representatives. The second part of the digital survey includes two validated questionnaires. The QUALAS is a validated questionnaire regarding quality of life in patients with spina bifida. There are two different versions for the ages 8-12 and 13-18 years. To evaluate sexuality the IIEF-5 (for boys) and the FSFI-6 (for girls) are used. These questionnaires are validated and are used in patients with spina bifida to evaluate sexual function as standard of care. Only children aged 13 years or older will be asked if they want to answer questions about sexuality and if they answer yes they will be asked for which gender they want to answer questions about their sexuality. After this they'll get the IIEF-5 or FSFI-6 questionnaire.

This digital survey is available in nine languages: English, Spanish, German, Italian, French, Danish, Greek, Turkish and Dutch.

The link to surveymonkey will be distributed by the IFSBH and local patient organizations among their members.

After the data have been collected, the general results of the survey will be evaluated and interpreted with a sounding board group. When patients participate with the digital survey they will not be involved in the sounding group. This sounding board group will consist of children/adolescents/adults with spina bifida who are representatives from the patient organization IFSBH and panel members of the EAU. This sounding board group will meet for a day. Finally, the results will be used to update the EAU Pediatric Urology guidelines.

5.2 This is a demographic study. Patients will not receive any difference in treatment.

5.3 The survey only has to be completed once and is completely voluntary. The questionnaire will take around 15 minutes to complete. It will not influence their own treatment.

5.4 There are no known risks of participating in the study given the fact that involves only the completion of questionnaires and data about standard of care. Also, all responses will be anonymous and completely voluntary. No personal identifying information will be used when reporting the data.

6 Unexpected discoveries

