For this aim we have developed a survey to evaluate the current organization of care, demographic features and received treatment. The outcome of this survey will show the exact differences in care between European countries. We have included two validated questionnaires to measure the effect this has on quality of life and sexuality. The information gathered will be used to adapt the clinical EAU Pediatric Urology guidelines.

2. Objective(s)

The main objective is to improve the quality of life of patients with spina bifida by updating the guidelines according to the differences found in care and how this impacts patients outcomes. We will evaluate the difference in organization of care between different European countries based on the outcomes of the primary survey. The baseline quality of life and sexuality reported will be evaluated with the QUALAS and the IIEF-5/FSFI-6 questionnaires [3-6]. We will then explore the relationship between how care is organized and how this affects quality of life and sexuality. The results of this study will be used to update the EAU Pediatric Urology clinical guidelines. Also, it will highlight the direction for future research to improve patients care and thereby quality of life and/or sexuality, which patients with spina bifida have stated they themselves find important.

3. Study type

3.1 Study type:

- Retrospective
- Prospective
- Combination Retrospective/Prospective

3.2 Check all the applicable boxes:

- Medical records (re-use of data from healthcare, including AI)
- Case report
- Re-use data from research
- Evaluations of quality of healthcare (retrospective)

QoL in patients with spina bifida

- Research with additional use of residual material from regular healthcare
- Research with re-use of human materials from research or existing biobank
- Research with human materials without biobank
- De novo biobank (human material obtained without burdensome or invasive procedures)
- Post marketing survey research with medical devices
- Phase IV research
- Healthcare evaluation research (prospective)
- Medical devices
- In Vitro Diagnostic Tests
- Other research, *describe*

4. Study population

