4.2 Inclusion criteria

In order to be eligible to participate in this study, a subject must meet all of the following criteria:

- Must have spina bifida
- Must be able to complete the digital survey, with help of caregivers allowed.
- Speak one of the nine available languages:
 - o English,
 - o Spanish,
 - o German,
 - o Italian,
 - o French,
 - o Danish,
 - o Greek,
 - o Turkish,
 - o Dutch

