6.1 Is there a chance of unexpected discoveries?

Yes

No

7 Exchange, sharing or transfer of data and/or human material and/or images outside Erasmus MC

The data will be collected and stored within the Erasmus MC in the Castor program. Only anonymous data will be collected and shared with collaborating colleagues from the EAU Pediatric Urology guidelines panel from their respective institutions outside the Erasmus MC. The institutions are:

- University of Leuven, Leuven, Belgium

- Medical University of Innsbruck, Innsbruck, Austria
- Hacettepe University, Ankara, Turkey
- University Medical Center Groningen, Rijks University Groningen, Groningen, The Netherlands
- Istanbul Biruni University, Istanbul, Turkey
- East of England Deanery, Urology, Cambridge, United Kingdom
- University of Medical Center Mannheim, Heidelberg University, Mannheim, Germany
- Aarhus University, Aarhus, Denmark
- Fondazione IRCCS Ca' Granda, Ospedale Maggiore Policlinico, Milan, Italy
- Pediatric Hospital Bambin-Gesù, Rome, Italy
- Radboud University Medical Center, Nijmegen, The Netherlands
- University of Zurich, Zurich, Switzerland
- Beacon Hospital, Dublin, Ireland

8 Statistical analysis

8.1 Main study parameter/endpoint:

The primary parameter is to evaluate quality of life in children with spina bifida using the QUALAS questionnaire. We will evaluate the differences in quality of life between European countries. Also, we will evaluate which demographic parameters are of influence on quality of life.
Descriptive statistics will be used.

8.2 Secondary study parameters/endpoints:

Secondary parameters will include sexual function using the outcomes of the IIEF-5/FSFI-6 questionnaires, also in relation to differences between European countries. Other parameters include organization of care, treatment received, treatment options available, which will all be extracted from the primary survey. Again descriptive statistics will be used.

9. Recruitment and consent

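### The plan as described names no disease-severity variable, so crude care and country differences in QUALAS would mix any effect of care with how affected the children are

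*Combined protocol and SAP*

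**What the plan says.** **Who enters.** On disease, Section 4.2 asks only "Must have spina bifida", and the matching exclusion in Section 4.3 is "Does not have spina bifida". Type, lesion level and functional level are not restricted.

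**What is collected.** Section 1 states: "For this aim we have developed a survey to evaluate the current organization of care, demographic features and received treatment". Section 5.1 repeats the same three domains: "This digital survey includes a primary survey regarding basic demographic features, medical treatment and organization of care". The validated QUALAS and IIEF-5/FSFI-6 questionnaires follow. The questionnaires are listed in Section 14 as an attachment, and their items are not reproduced in the protocol text.

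**What is analysed.** Section 8.1 compares QUALAS between European countries and adds: "Also, we will evaluate which demographic parameters are of influence on quality of life". Section 8.2 covers sexual function, also by country, and then: "Other parameters include organization of care, treatment received, treatment options available, which will all be extracted from the primary survey". Both sections specify descriptive statistics.

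**What is to be concluded.** Section 2 says: "We will then explore the relationship between how care is organized and how this affects quality of life and sexuality". It then directs the results to the EAU Pediatric Urology guidelines.

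**How often.** Section 5.3: "The survey only has to be completed once and is completely voluntary". Sections 9.1 and 10.1 say that responses cannot be traced to an individual.

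**The concern.** Treatment and intensity of care plausibly follow need. More affected children are likely to see more specialists and receive more treatment, and they may also report lower quality of life because of the condition itself. If the share of more affected children differs between care arrangements, a crude QUALAS comparison picks up that difference as though it came from the care. The same happens between countries if patient organisations reach different mixes of children.

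The purely descriptive aims, such as quality of life in those who responded or how care is organised in each country, do not need severity adjustment. The aim at stake is the Section 2 relation between care and outcome, together with the guideline use built on it. More responses would not help, because they narrow the interval around a biased figure. Nor can the gap be closed afterwards, since anonymous respondents cannot be recontacted or linked to records.

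**Working it through.** **Step 1. Aim against plan.**

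- *Aim (Section 2):* relate the organisation of care to quality of life and sexuality, in causal wording.
- *Entry (4.2, 4.3):* all forms of spina bifida.
- *Survey content (1, 5.1):* demographics, treatment and organisation of care. Neither description names a severity variable.
- *Analysis (8.1, 8.2):* QUALAS by country and demographics; sexual function by country; care and treatment as further descriptive parameters. No table crossing care with QUALAS is specified, and no stratification or adjustment.

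The care-to-outcome aim thus has neither a stated analysis nor a named variable that would separate care from severity. The treatment items may partly stand in for severity. But treatment is also part of the care being compared, so adjusting for it would not cleanly remove the confounding.

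**Step 2. Possible size.** The plan has no figure to reproduce. The target of 500 in Section 4.4 is an aim without a calculation, and no SD or effect size is given. Everything below is assumed, with no true effect of care:

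false difference (SD) = (difference in share of more affected children) x (QUALAS gap between more and less affected children, in SD)

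| Imbalance in share | Gap 0.3 SD | Gap 0.5 SD | Gap 0.8 SD |
|---|---|---|---|
| 10 points | 0.03 | 0.05 | 0.08 |
| 20 points | 0.06 | 0.10 | 0.16 |
| 30 points | 0.09 | 0.15 | 0.24 |
| 50 points (80% v 30%) | 0.15 | 0.25 | 0.40 |

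A 20-point imbalance could arise between two countries with 60% and 40% more affected children. The 50-point row is a large imbalance, of the kind that might separate children with and without a given treatment.

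**Step 3. Comparison with sampling error.** Assume that 500 responses split 250/250, with SD 1. The standard error is sqrt(2/250) = 0.089 SD. A two-sided 5% comparison would then detect (1.96 + 0.84) x 0.089 = 0.25 SD with 80% power. The plan proposes no such test; it serves only as a yardstick. With no true effect, false differences of 0.03, 0.10 and 0.24 SD would reach nominal significance in about 6%, 20% and 77% of repetitions. The bias formula contains no sample size, so it does not shrink with recruitment.

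**Step 4. What stratification costs in cell size.** Assume 10 countries, since the documents give no number. Then 500/10 = 50 per country; an even split between the two QUALAS versions gives 50/2 = 25; an even split into two severity strata gives 25/2, about 12. That is before any split by care arrangement, so strata must be broad and some pooling is likely.

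**The case against.** The strongest reply is that the study calls itself descriptive, uses the word explore, and relies on a questionnaire that is not in the protocol text. Several parts of this stand.

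- **Severity not recorded.** A reader might infer that the survey collects none. The documents do not show that. The survey summaries are one sentence each, the questionnaire is an attachment that was not available, and demographic parameters are not itemised. What can be said is that the text names no severity variable and Section 8 uses none.
- **A planned misleading result.** A reader might infer that Section 8, followed as written, would show intensive care going with worse scores. Section 8 does not cross care with QUALAS; only the Section 2 aim implies that comparison. Of the QUALAS comparisons at issue, the country comparison is the one actually specified.
- **Sign reversal.** A reader might infer that the bias would make beneficial care look harmful. That is possible in principle, but the documents give no effect sizes and the illustration assumes no true effect, so it is not shown.
- **Shunt and continence as strata.** They look like natural severity markers. Either may be part or a result of the care compared, and stratifying on them could remove some of its effect.
- **Minimum time under current care.** One survey records care and outcome together, so a restriction such as 12 months may seem to follow. The documents offer no basis for a cut-off.
- **Broad eligibility.** Admitting every form of spina bifida is reasonable for a descriptive survey and is not itself a fault.

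The descriptive label does not remove the remaining problem, because Section 2 uses causal wording and sends the result to a guideline.

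**Conclusion.** The point holds in limited form. The plan combines an all-comers sample with a care-to-outcome aim, while naming no severity variable in the survey description and assigning none in Section 8. Crude care and country differences in QUALAS therefore cannot be read as effects of care.

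The size is unknown. Under the assumed inputs it ranges from 0.03 SD, which is negligible, to 0.40 SD, which exceeds the 0.25 SD that two groups of 250 would detect with 80% power. Without a severity variable, nobody could tell afterwards which case applied. The conclusion rests on two assumptions: that severity is related to QUALAS, and that it differs between the groups compared. Both are plausible, but neither is quantified in the documents. If the questionnaire already holds severity items, the collection gap disappears, but the gap in Section 8 and the causal wording remain. This should be corrected; it does not undermine the purely descriptive aims.

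**What to change.** 1. **Section 5.1.** Confirm whether the questionnaire already records severity, and say so. If it does not, add two or three closed items that families can answer and that are not themselves part of the care compared, such as type or level of lesion if known, and walking ability.
2. **Sections 8.1 and 8.2.** Show QUALAS by country and by organisation of care within broad severity strata (for example walking versus wheelchair use), beside the crude figures. Where cells are small, pool countries or use a simple comparison adjusted for severity and age.
3. **Section 2.** Replace *affects* with *is associated with*, and state that crude care or country differences will not be read as effects of care.

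**Cost.** About one extra minute on a survey of around 15 minutes, and translation of the items into nine languages. If the NWTC has already given its opinion, Section 11 requires the change to be submitted as an amendment, with approval first if it is substantial. Cells become smaller, as Step 4 shows. Family-reported severity is imperfect, so confounding is reduced, not removed. If the survey can no longer be changed, the third step still applies and costs almost nothing.

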Primary outcome will be the quality of life in children and adolescents with spina bifida. We will evaluate if their demographic differences influence the quality of life and if differences are seen between the different European countries. Secondary outcomes include differences in sexual function, organization of care, treatment received, treatment options available, with also a focus on differences between the different European countries.

The results of this survey will be evaluated and interpreted within a sounding board group consisting of children/adolescents/adults with spina bifida, patient representatives from IFSBH and panel members of the EAU Pediatric Urology guidelines panel. Finally, the interpreted results will be used to update the EAU Pediatric Urology guidelines to make these more patient centered.

There are no known risks of participating in the study given the fact that participation includes only completion of questionnaires and data about standard of care. Furthermore, the study is completely voluntary and the results will be completely anonymous.

1. Introduction and rationale

Children with spina bifida require care from various medical and paramedical specialists throughout their life. The availability and organization of the care needed differs between the European countries. It can be expected that this variety results in differences in outcome of care.

Children with spina bifida have stated that for future research they feel it is important that quality of life and sexuality are investigated. [1]

The EAU Pediatric Urology guidelines panel wants to ensure that patients with spina bifida receive the best possible care based on the best available clinical evidence. [2] Additionally, we want to improve the clinical guidelines by including patients perspectives. The IFSBH represents patients with spina bifida and values the promotion and protection of the human rights of patients with spina bifida thereby improving quality of life.

Together with the IFSBH we have set up a collaboration to investigate how we can make the guidelines more patient centered and thereby improve quality of care and quality of life.

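### Does the primary quality-of-life analysis need a stated rule for combining the two age versions of the QUALAS?

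*Combined protocol and SAP*

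**What the plan says.** Sections 4.1 and 4.3 define a single population aged 8 to 18. Section 5.1 says of the QUALAS: "There are two different versions for the ages 8-12 and 13-18 years". References 3 and 4 give a separate paper for the child version (QUALAS-C) and the teenage version (QUALAS-T), and section 2 cites references 3 to 6 together for its outcome measures.

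The protocol summary states: "Primary outcome will be the quality of life in children and adolescents with spina bifida". Section 8.1 states: "The primary parameter is to evaluate quality of life in children with spina bifida using the QUALAS questionnaire". It adds two uses of that parameter: "We will evaluate the differences in quality of life between European countries", and "Also, we will evaluate which demographic parameters are of influence on quality of life". The only method named is descriptive statistics. Neither the summary, section 2, section 8.1 nor section 8.2 says whether QUALAS results are given by version, pooled, rescaled or stratified. Section 8.1 also names no score or domain.

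**The concern.** The population spans both versions, yet the primary parameter is described as if one questionnaire served everyone. If raw scores from both versions were averaged and the versions ran on different scales, part of any difference between countries could reflect how many teenagers answered in each. A comparison of children with teenagers would be fully confounded with version, because the two coincide at the 12/13 boundary.

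The results are meant to inform the EAU guidelines, and section 2 also intends to relate quality of life to the organization of care: "We will then explore the relationship between how care is organized and how this affects quality of life and sexuality". Recruitment is by open link through patient organizations with no age quota, so nothing in the design forces the age mix to be equal across countries.

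**Working it through.** There is no figure in the plan to reproduce. The aim of 500 in section 4.4 is a target without a calculation behind it. The check therefore has two parts: what the text implies, and how large the effect could be under stated assumptions.

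**Text.** Bias from pooling needs two conditions: scores are pooled, and the versions differ in scale. No section states either. In favour of separate reporting, section 5.1 splits the instrument by age, references 3 and 4 support each version with its own paper, and section 2 ties both papers to the outcome. Section 8.1 uses the family name QUALAS, which covers both versions.

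**Assumed inputs (none is in the documents).**
- Offset between versions, d: 0 to 0.5 SD
- Ages uniform over the 11 integer years 8 to 18
- 50 respondents per country
- Difference between two countries in the share aged 13-18, s: 20 or 40 percentage points

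**Split by version.** Share aged 13-18 = 6/11 = 0.545. Of 500, about 273 would be 13-18 and 227 would be 8-12. Of 50 in a country, about 27 and 23.

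**Precision of a two-country contrast.** SE = sqrt(2/50) = 0.200 SD.

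**Shift from pooling = d × s.**
- d = 0: no shift at any s
- d = 0.2, s = 0.2: 0.04 SD = 0.2 SE
- d = 0.5, s = 0.2: 0.10 SD = 0.5 SE
- For a shift of one SE, s = 0.200/d: 0.40 at d = 0.5, and 1.00 at d = 0.2

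**Equal age mix.** There is no systematic shift. Pooling only inflates the SD by sqrt(1 + d² × 0.545 × 0.455), which is 1.005 at d = 0.2 and 1.031 at d = 0.5.

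**What separation costs.**
- Within version, at 23 and 27 per country: SE = sqrt(2/23) = 0.295 and sqrt(2/27) = 0.272 SD
- Combined but stratified by version, SE = 1/sqrt(sum over versions of nA·nB/(nA + nB)):
  - equal shares: 0.200
  - 60% against 40%: 1/sqrt(12 + 12) = 0.204
  - 70% against 30%: 1/sqrt(10.5 + 10.5) = 0.218

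**Bias and precision together, at d = 0.5 and shares 60% and 40%.** The pooled contrast has SE = sqrt((1 + 0.25 × 0.24) × 2/50) = 0.206 and bias 0.10, so its root-mean-square error is sqrt(0.206² + 0.10²) = 0.23 SD. That is smaller than the within-version SE, which at these shares is sqrt(1/30 + 1/20) = 0.29 SD. A stratified combined figure, at 0.204, improves on both.

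**The case for a change.** The strongest case for a change is that a descriptive mean still needs a rule on which scores enter it. Fixing the rule in advance prevents a choice guided by the results, and it would take only a sentence. The gap stands as a fact: the text supplied contains no such rule.

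Two textual arguments are offered for a pooled reading, and neither holds. Section 1 says "We have included two validated questionnaires to measure the effect this has on quality of life and sexuality", which appears to count the QUALAS as one instrument. But to reach that count, the IIEF-5 and FSFI-6 must also be taken as one, although section 5.1 offers them as alternatives by gender. The phrase counts topics and says nothing about analysis. Second, section 8.2 names both of its forms ("Secondary parameters will include sexual function using the outcomes of the IIEF-5/FSFI-6 questionnaires") while 8.1 names neither QUALAS version. The IIEF-5 and FSFI-6 have different names and must be listed, whereas the two QUALAS versions share one.

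The absence of an age quota does leave age mix free to vary between countries. That supplies one ingredient of a bias, not the pooling or the scale difference it also requires. The questionnaires and the Data Management Plan appear in the list of attachments but were not in the text reviewed, so a scoring rule there cannot be excluded.

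**Conclusion.** No change is called for. The plan leaves out a reporting detail but states no rule that would give a wrong result. An analyst holding two age-specific forms, each with its own validation paper, would ordinarily tabulate them by version and stratify any combined country figure. Age determines version, so this remains possible after collection and loses no data. Section 4.4 describes the study as descriptive with no minimum sample size, so no test or sample size depends on the choice.

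Under the assumptions above, the worst illustrated shift in a country contrast at a 20-point share gap is 0.10 SD, half a standard error. It is zero if the scales match or the age mix is equal. A child-teenager contrast would absorb the whole assumed offset, but section 8.1 does not list age among its comparisons. Separate reporting would not recover that contrast either, because version and age group cannot be told apart. These sizes are illustrative only. The conclusion rests mainly on the text showing neither pooling nor a difference in scale.

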12. Publication	11
13. References	11
14. Attachments	12

LIST OF ABBREVIATIONS AND RELEVANT DEFINITIONS*

CTA	Clinical Trial Agreement
De novo biobank	The information of a new data, human material or imaging collection
DMP	Data Management Plan
DPIA	Data Protection Impact Assessment
DTA	Data Transfer Agreement
EAU	European Association for Urology
Exception consent	Form Care for data Template , in Dutch: Formulier uitzondering toestemming
FSFI-6	Female Sexual Function Index – 6
GCP	Good Clinical Practice
GDPR	General Data Protection Regulation in Dutch: Algemene Verordening Gegevensbescherming
IC	Informed Consent
IFSBH	International Federation for Spina Bifida and Hydrocephalus
IFU	Instruction For Use
IIEF-5	International Index of Erectile Function – 5
MTA	Material Transfer Agreement
NWTC	Non-WMO Review Committee; in Dutch: Niet WMO Toetsingscommissie
QUALAS	QUALity of Life Assessment in patients with Spina bifida
UAVG	Dutch Act on Implementation of the General Data Protection Regulation; in Dutch: Uitvoeringswet Algemene Verordening Gegevensbescherming
WMO	Medical Research Involving Human Subjects Act, in Dutch: Wet Medisch-wetenschappelijk Onderzoek met Mensen

**Please delete abbreviations/definitions that are not applicable and add any new ones that are used in the research protocol*

PROTOCOL SUMMARY

Children with spina bifida require care from various medical and paramedical specialists throughout their life. The availability and organization of the care needed differs between the European countries. The EAU and IFSBH are both organizations with the aim to improve patient care and clinical outcomes for children with spina bifida.

We have set up a collaboration to evaluate the differences in organization of care and clinical treatment received and how this affects outcomes with regard to quality of life and sexuality.

A digital survey has been constructed which will be distributed among children and adolescents with spina bifida and their caregivers. The IFSBH and national patient organizations will send out invitations to their members. Children and adolescents from 8 – 18 years of age with spina bifida are eligible for inclusion.

The survey includes a primary survey developed in collaboration between panelmembers of the EAU pediatric urology guidelines and patient representatives. The second part includes validated questionnaires to evaluate Quality of life with the QUALAS and sexual function with the IIEF-5/FSFI-6 for boys/girls respectively.

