9.1 Will the subjects be asked for informed consent?

Yes (*Upload Patient Information Letter and Informed Consent*)
 No, only anonymous data is used, i.e. the data can never be traced back to an individual subject
 No, this research will be performed under the exception consent
(Upload form Care for data Template, in Dutch: Formulier uitzondering toestemming)
 Other (e.g. partly, indirectly) *Please describe the situation*
The digital survey that has been constructed by the EAU and IFSBH will be distributed through the IFSBH and local patient organizations to their members by email and newsletter. A link to the digital survey can be found in this correspondence.

A short introduction with the purpose of the survey and a question whether patients agree that their data will anonymously be used for research is the start of the digital survey. When patients answer no to this question, the digital survey is immediately ended. The data gathered cannot be traced back to the individual respondents.

9.2 If no, exception consent: Participation is voluntary, people that do not want to participate will not complete the questionnaire. They can withdrawal at any time and the responses will be deleted.

10. Handling and storage of data and images

10.1 The data is collected anonymous and it will not be possible to trace back to one specific patient.

10.2 The data will be stored in the Castor information system. Only anonymous data will be used, so it will not be possible to trace back to an individual patient.

11. Amendments

Amendments are changes made to the research after a favourable opinion by the NWTC has been given. All amendments will be submitted to the NWTC that gave the favourable opinion.

Substantial amendments must be approved by the NWTC before they can be implemented.

12. Publication

Do you have the intention to submit the study results in a manuscript for publication in a journal:

Yes

No, *please motivate*

13. References

2. Radmayr C, et al: EAU Pediatric urology guidelines, EAU Guidelines. Edn. presented at the EAU Annual Congress Amsterdam 2022. ISBN 978-94-92671-16-5

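### One anonymous survey link reaches children and caregivers through several organisations, so a child can be entered more than once, and the protocol describes no rule of one survey per child

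*Combined protocol and SAP*

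**What the plan says.** Section 5.1 describes a single SurveyMonkey address and says: "The link to surveymonkey will be distributed by the IFSBH and local patient organizations among their members". No personal token or invitation code is mentioned. Section 9.1 gives the medium: the survey "will be distributed through the IFSBH and local patient organizations to their members by email and newsletter". The Protocol Summary names the recipients: "A digital survey has been constructed which will be distributed among children and adolescents with spina bifida and their caregivers".

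Section 4.2 lets caregivers help with completion. Sections 5.4, 9.1, 10.1 and 10.2 make the responses anonymous, and 9.1 and 10 add that they cannot be traced to a person. Section 4.6 keeps the survey open for three months.

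The only statement on repetition is in section 5.3: "The survey only has to be completed once and is completely voluntary". Section 4.4 sets the target: "However, our aim is to include 500 patients". Sections 8.1 and 8.2 plan descriptive statistics for QUALAS, by country and by demographic factor, and for the secondary parameters. Neither those sections nor the eligibility criteria in 4.2 and 4.3 mention duplicate entries.

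**The concern.** The target is counted in patients, but the survey collects responses. The two agree only if each child is entered once, and nothing in the protocol secures that. A family that belongs to both a national organisation and the international federation may receive the link twice. A teenager and a parent may each receive it and each answer. Section 5.3 sits beside the remarks on voluntary participation and the 15-minute completion time. It tells respondents how little is asked of them; it does not limit entries.

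Two things are at stake. The reported number of patients could be too high, and children entered twice would count double in the country and demographic summaries of quality of life, which are meant to inform a guideline update. A country with few responses would be the most sensitive to a handful of repeats. Because records are anonymous by design, the information needed to recognise a repeat has to be asked for at entry.

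**Working it through.** **The plan's own figure.** The 500 in section 4.4 cannot be reproduced. It is an aim without inputs, and the section says: "Since this is a descriptive study no minimal sample size is required". It serves below only as the number of responses.

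**Inputs.** N = 500 responses (section 4.4). Let f be the share of responses that are second entries for a child already entered, and ρ the correlation between a child's two records. The documents give neither, so both are assumptions. No child is taken to be entered more than twice.

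**Children represented.** Of 500 responses, 500f are second entries, so there are 500(1 − f) children: 500f entered twice and 500(1 − 2f) entered once.

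**Standard error, if one is ever reported.** With identical repeats (ρ = 1), the variance of the mean in units of σ² is [500(1 − 2f) + 4 × 500f] / 500² = (1 + 2f)/500. The true standard error is therefore √(1 + 2f) times the naive one. For general ρ the factor is √(1 + 2fρ), so ρ = 1 gives the upper bound.

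| f (assumed) | Children in 500 responses | SE factor, ρ = 1 | SE factor, ρ = 0.6 | Effective n, ρ = 1 |
|---|---|---|---|---|
| 5% | 475 | √1.10 = 1.05 | √1.06 = 1.03 | 455 |
| 10% | 450 | √1.20 = 1.10 | √1.12 = 1.06 | 417 |
| 20% | 400 | √1.40 = 1.18 | √1.24 = 1.11 | 357 |

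**Check with the rate defined per child.** If a share d of children is entered twice, there are 500/(1 + d) children and the variance inflation is 1 + 2dρ/(1 + d). This is the same formula with f = d/(1 + d). For d from 2% to 20% and ρ from 0.6 to 1.0, the 500 responses hold 490 down to 417 children. A naive 95% interval would be 1.2% to 13.4% too narrow, with coverage from 94.7% down to 91.0%. A simulation at d = 10%, ρ = 1 gave 93.0% coverage against 92.9% from the formula.

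**Weight in a mean.** Children entered twice make up f/(1 − f) of the children but 2f of the responses. At f = 20% that is 100/400 = 25% of children carrying 200/500 = 40% of the weight. If they differ from the others by 0.5 SD (an assumption), the mean moves by (0.40 − 0.25) × 0.5 = 0.075 SD. At f = 5% the shares are 25/475 = 5.3% and 10%, and the shift is 0.024 SD. For scale, a 95% half-width at n = 500 is 1.96/√500 = 0.088 SD. If repeats occur at random with respect to quality of life, the expected shift is zero.

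**Can repeats be found afterwards by matching?** Suppose 500 distinct children were spread evenly over 10 countries, 11 ages and 2 genders (assumed). There are 500 × 499/2 = 124,750 pairs and 10 × 11 × 2 = 220 cells, so about 124,750/220 = 567 pairs of different children match by chance. Adding 5, 20 or 50 equally common treatment patterns leaves about 113, 28 or 11 chance pairs. An uneven spread gives more. At f = 5% there are only 25 true repeats, so false matches could equal or outnumber them.

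**The case against.** The strongest reply is that this is a general limit of open surveys, that no duplication has been shown, and that the consequence is small. Much of that stands.

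- **Repeats are possible, not demonstrated.** No rate is given and no incentive to repeat is described. The caregiver's role in section 4.2 is to help, which fits one jointly completed form. Membership overlap between organisations is plausible but not stated.
- **A reader might infer that the planned intervals will be too narrow.** The documents do not support this. Sections 8.1 and 8.2 plan descriptive statistics only and name no interval, standard error, test or model. The narrowing applies only if intervals are reported later, and it is modest at low rates.
- **A reader might infer that every response will be analysed as a separate patient.** The plan does not say so; it is silent.
- **A reader might infer that no control exists anywhere.** That cannot be established. The questionnaires and Data Management Plan appear only in the list of attachments (section 14), and neither the survey's opening page nor its platform settings are reproduced.

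What the reply does not remove is the gap in the protocol itself: several senders, two kinds of recipient, untraceable records and no one-per-child rule. Nor can the analysts close that gap later, because matching on recorded attributes is too unreliable.

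**Conclusion.** The point holds as a cheap improvement to make before launch. The same child can be entered more than once, the protocol describes nothing to prevent it, and repeats could not be reliably identified after anonymous collection. For the results actually planned, the direct effects are an inflated patient count and extra weight on double-entered children in the country and demographic QUALAS summaries.

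The size is unknown. The 5% to 20% scenarios are assumptions, and the standard-error factors of 1.05 to 1.18 are upper bounds that require identical repeats. The shift in a mean requires, in addition, that double-entered children differ from the rest. The documents do not support a statement that patients are in fact being double-counted.

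**What to change.** Before launch:

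1. State on the first page of the survey, and in sections 5.1 and 5.3, that one survey is to be completed per child.
2. Add the question *Has a survey already been completed for this child?* and end the survey if the answer is yes. Word it per child, so that a second affected sibling can still take part.
3. Ask who is answering: the child, a caregiver, or both together.
4. Use the platform's one-response-per-device setting only if it is compatible with the anonymity commitment in sections 5.4, 9.1 and 10 and does not block affected siblings.

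If the questionnaires or Data Management Plan already contain such a control, a reference to it in section 5 is enough for that item. Do not rely on deleting the later of two records that agree on country, age, gender and treatment items: this would remove genuine children and might discard the child's own answers in favour of the caregiver's.

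The cost is one sentence and two short questions in nine languages. The questions rely on honest answers and on the respondent knowing of an earlier entry, so they reduce repeats without excluding them.
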